9.3 Populations for Analysis

The following populations are defined:

Population	Description
Enrolled	All subjects who sign the ICF
Safety	The Safety Analysis Set will consist of all subjects who received at least 1 dose of any Investigational Products. The analysis of all safety and efficacy endpoints, unless noted otherwise, will be conducted on the Safety Analysis Set.
DLT	For the dose exploration part of the study, the analysis of DLT will be conducted on the DLT Analysis Set, defined as all subjects that are enrolled and received at least 1 dose of tarlatamab and AMG 404 with an evaluable DLT endpoint. The DLT endpoint is evaluable if either: 1) the subject experiences a DLT, or 2) the subject does not experience a DLT and receives tarlatamab and AMG 404 treatment as

98

[figure not shown]
Protocol Number: 20200439

Date: 05 June 2024 Page 107 of 176

	planned in cycle 1 and has been followed for safety events a minimum of from start of treatment.
OR	The OR Analysis Set will consist of all subjects in the Safety Analysis Set who have had the opportunity to be followed for at least 8 weeks starting from day 1.
PK	The PK Analysis Set will contain all subjects who have received at least 1 dose of the Investigational Product and have at least 1 PK sample collected. These subjects will be evaluated for PK analysis unless the number of data points required for analysis is not enough, or significant protocol deviations have affected the data, or if key dosing or sampling information is missing.

9.3.1 Covariates

The relationship between covariates and efficacy endpoints may be explored if appropriate.

9.4 Statistical Analyses

The statistical analysis plan will be developed and finalized before database lock. Below is a summary of the timing and methods for the planned statistical analyses. To preserve study integrity, the final analysis will be conducted and reported following the end of study, as defined in Section 4.5.

9.4.1 Planned Analyses

9.4.1.1 Interim Analysis and Early Stopping Guidelines

Safety data will be reviewed on an ongoing basis.

During dose exploration (Part 1) and formally during DLRMs, Amgen, in consultation with the site investigators, will review all available cumulative data by cohort prior to making dose escalation or dose de-escalation recommendation. Adverse events and DLTs observed in all subjects will be evaluated continually and fully integrated into all DLRMs and considered in all enrolment and dosing decisions.

Protocol Number: 20200439

Date: 05 June 2024 Page 108 of 176

During dose expansion (Part 2), Amgen will conduct evaluations of the ongoing grade 4 or higher treatment-related **treatment emergent adverse events** to assess if the threshold for possible early trial termination has been reached. The safety interim will occur for every subjects enrolled who have had opportunity to have at least days of follow up since the first dose of tarlatamab. If this threshold is met, enrollment to dose expansion will be halted pending review of safety data by the DLRT. After receiving the DLRT recommendation, Amgen will choose to take one of the following actions.

- 1) Terminate the trial
- 2) Amend the protocol to potentially improve the benefit/risk for subjects (eg, increase safety monitoring, modify dose/schedule, mandate premedication)
- 3) Continue dose expansion without any changes.

The stopping rules use a Bayesian approach proposed by Thall (Thall et al, 1995) to terminate the study if the posterior probability that the grade 4 or higher treatment-related **treatment emergent adverse event** rate is greater than 20% is > 80%. The stopping boundaries assume a prior distribution of Beta (0.40, 1.60) are presented in Table 9-2 and the operating characteristics with pre-specified batch size of new subjects per batch are presented in Table 9-3.

Table 9-2. Stopping Boundary for Dose Expansion with Posterior Probability of 80% and Grade 4 or Higher Treatment-related Adverse Event Limit of 20%

Number of Subjects	Stop Subjects if Observing This Many Grade 4 or Higher Treatment-related Adverse Events	
	≥ 4	
	≥ 6	
	≥ 9	
	Dose Expansion Complete	

Table 9-3 Operating Characteristics with Batch Size of Subjects

True Grade 4 or Higher Treatment-related Adverse Event Rate	Probability of Early Stopping of Dose Expansion	Average Dose Expansion Sample Size
0.10	2.0%	39.5
0.15	9.7%	37.6
0.20	25.8%	33.9
0.25	47.7%	28.8

Protocol Number: 20200439

Date: 05 June 2024 Page 109 of 176

0.30	69.2%	23.4
------	-------	------

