9.4.1.1.1 Criteria for Evaluating Treatment With Siltuximab

Amgen will conduct evaluations of the treatment and outcome of the CRS events treated with siltuximab on an ongoing basis to assess if the threshold for evaluating siltuximab treatment has been reached as outlined in the Table 9-4. If these criteria are met, an adhoc DLRM will be triggered to review safety data and available pharmacokinetic, pharmacodynamics, and efficacy data. If recommended by DLRT, the use of siltuximab will resume. The criteria to trigger an adhoc DLRM to review siltuximab treatment use a Bayesian approach proposed by Thall et al, 1995; an adhoc DLRM will be triggered if the posterior probability that the CRS progression to grade 3 rate of greater than 20% is > 80% or the posterior probability that the CRS progression to grade 4 rate of greater than 7.5% is >80%; or observation of any grade 5 CRS after the event has been treated with siltuximab. The boundaries presented below assume a prior distribution of Beta (0.4, 1.6) for progression to grade 3 CRS and a prior distribution of Beta (0.4, 1.6) for progression to grade 4 CRS. The evaluations could occur more frequently if necessary to address emerging safety concerns. If the triggered ad hoc DLRM coincides with regular DLRM, they may be combined.

Table 9-4. The Criteria for Evaluating the Use of Siltuximab

	Trigger DLRM if severity of any CRS event treated with siltuximab progresses to Grade 5					
Number of subjects treated with siltuximab	Or this number of subjects with severity of CRS progressed to Grade 3 after being treated with siltuximab	Or this number of subjects with severity of CRS progressed to Grade 4 after being treated with siltuximab				
	≥ 3	≥ 2				
	≥ 4	≥ 2				
	≥ 5	≥ 3				
	≥ 6	≥ 3				
	≥ 7	≥ 4				
	≥ 9	≥ 4				
	≥ 10	≥ 5				
	≥ 11	≥ 5				

CRS = cytokine release syndrome; DLRM = Dose Level Review Meeting

Protocol Number: 20200439

Date: 05 June 2024 Page 110 of 176

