Examples of such events include invasive or malignant cancers, intensive treatment in an emergency room or at home for allergic bronchospasm, blood dyscrasias or convulsions that do not result in hospitalization, or development of drug dependency or drug abuse.

Recording Adverse Events and Serious Adverse Events

Adverse Event and Serious Adverse Event Recording

- When an adverse event or serious adverse event occurs, it is the responsibility of the investigator to review all documentation (eg, hospital progress notes, laboratory, and diagnostics reports) related to the event.
- The investigator will then record all relevant adverse event/serious adverse event information in the Event case report form (CRF).
- The investigator must assign the following mandatory adverse event attributes:
 - Adverse event diagnosis or syndrome(s), if known (if not known, signs or symptoms);
 - Dates of onset and resolution (if resolved);
 - Did the event start prior to first dose of investigational product, other protocolrequired therapies;
 - Assessment of seriousness;
 - Severity (or toxicity defined below);
 - Assessment of relatedness to investigational product(s) and other protocol-required therapies.
 - Assessment of relatedness to study-required activity and/or procedures is only required for serious adverse events.
 - Action taken; and
 - Outcome of event.
- If the severity of an adverse event changes from the date of onset to the date of resolution, record as a single event with the worst severity on the Event CRF.

Protocol Number: 20200439

Date: 05 June 2024 Page 139 of 176

• It is not acceptable for the investigator to send photocopies of the subject's medical records to sponsor/responsible contract research organization (CRO) in lieu of completion of the Event CRF page.

- If specifically requested, the investigator may need to provide additional follow-up
 information, such as discharge summaries, medical records, or extracts from the
 medical records. In this case, all subject identifiers, with the exception of the
 subject number, will be blinded on the copies of the medical records before
 submission to Amgen.
- The investigator will attempt to establish a diagnosis of the event based on signs, symptoms, and/or other clinical information. In such cases, the diagnosis (not the individual signs/symptoms) will be documented as the adverse event/serious adverse event.

Evaluating Adverse Events and Serious Adverse Events

Assessment of Severity

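### The Part 2 safety boundary is printed as a count of adverse events, but its limits and operating characteristics hold only for a count of subjects

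*Protocol*

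**What the plan says.** Protocol 9.4.1.1 and SAP 7.1 set the formal Part 2 safety rule. The criterion is a posterior probability that the grade 4 or higher treatment-related event "rate is greater than 20% is > 80"%. On the prior, the protocol says: "The stopping boundaries assume a prior distribution of Beta (0.40, 1.60) are presented in Table 9-2".

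Table 9-2 sets a column of subject numbers (redacted) against limits of 4, 6 and 9, headed "Stop Subjects if Observing This Many Grade 4 or Higher Treatment-related Adverse Events". Its last row reads "Dose Expansion Complete". SAP Table 4 carries the same heading and limits. Protocol Table 9-3 and SAP Table 5 give early-stopping probabilities of 2.0%, 9.7%, 25.8%, 47.7% and 69.2% at true rates of 0.10, 0.15, 0.20, 0.25 and 0.30.

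If the limit is met, "enrollment to dose expansion will be halted pending review of safety data by the DLRT". The sponsor may then terminate, amend or continue unchanged. Neither section says that a subject with several qualifying events counts once.

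The siltuximab table in the next protocol subsection (Table 9-4) uses the same Bayesian method and does name the unit: "Or this number of subjects with severity of CRS progressed to Grade 3 after being treated with siltuximab".

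**The concern.** A beta-binomial boundary compares a number of affected subjects with a number of treated subjects. The heading asks instead for a number of events. A subject with two distinct grade 4 related events adds one to the first count and two to the second. Whoever applies the table as worded uses limits that were not derived for that count, and the printed operating characteristics no longer describe what is being done.

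This is the plan's formal stopping boundary for expansion, and safety is the primary objective. The study report will have to say whether the boundary was reached at each interim, and the answer can differ between the two counts.

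**Working it through.** **Inputs.** The prior Beta(0.40, 1.60), the 20% limit, the 80% cutoff, the limits 4/6/9 and the Table 9-3 figures are from Protocol 9.4.1.1 (repeated in SAP 7.1). The look times, batch size and maximum are redacted and are inferred in step 1. The number of qualifying events per affected subject is not in either document. It is assumed, with mean m from 1.0 to 2.0.

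**Step 1: the limits, counting subjects.** With x affected among n, the posterior is Beta(0.40 + x, 1.60 + n − x). The limit is the smallest x with P(p > 0.20) > 0.80.

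| n | x just below the limit | P(p > 0.20) | x at the limit | P(p > 0.20) |
|---|---|---|---|---|
| 10 | 3 | 0.719 | 4 | 0.895 |
| 20 | 5 | 0.666 | 6 | 0.826 |
| 30 | 8 | 0.783 | 9 | 0.885 |

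The limit is 4 for n = 9 to 12, 6 for n = 17 to 20 and 9 for n = 30 to 33. A batch of 9 gives 4/6/8 and a batch of 11 gives 4/7/9, so 10 is the only equal batch size that yields 4/6/9.

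**Step 2: the operating characteristics, counting subjects.** This is an exact sequential binomial calculation with looks at 10, 20 and 30. Average N = 10·P(halt at 10) + 20·P(halt at 20) + 30·P(halt at 30) + 40·P(no halt). At a true rate of 0.20: 10 × 0.1209 + 20 × 0.1109 + 30 × 0.0262 + 40 × 0.7421 = 33.9.

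| True rate | Halt, computed | Halt, Table 9-3 | Average N, computed | Average N, Table 9-3 |
|---|---|---|---|---|
| 0.10 | 2.05% | 2.0% | 39.5 | 39.5 |
| 0.15 | 9.7% | 9.7% | 37.6 | 37.6 |
| 0.20 | 25.8% | 25.8% | 33.9 | 33.9 |
| 0.25 | 47.7% | 47.7% | 28.8 | 28.8 |
| 0.30 | 69.2% | 69.2% | 23.4 | 23.4 |

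The agreement in average N also supports the maximum of 40. The published figures are per-subject figures.

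**Step 3: direction of the discrepancy.** Every affected subject has at least one event, so the event count is never below the subject count at any look. Any sequence of outcomes that halts on subjects also halts on events, at the same look or earlier. The literal reading can therefore only equal or exceed the stated halting probability.

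**Step 4: size of the discrepancy.** Each affected subject is given 1 + Poisson(m − 1) events, and the total is compared with the same 4/6/9 limits.

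| True subject rate | m = 1.0 | 1.1 | 1.25 | 1.5 | 2.0 |
|---|---|---|---|---|---|
| 0.10 | 2% | 5% | 10% | 20% | 38% |
| 0.15 | 10% | 17% | 28% | 43% | 64% |
| 0.20 | 26% | 36% | 50% | 65% | 83% |

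At a true rate of 0.20 the average N falls from 33.9 to 31.4, 28.1, 24.1 and 19.2 across the same means. Replacing the Poisson extra events by a geometric number changes the halting probabilities by about 3 points at most.

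**The case against.** The best reply is that the unit is already clear to a statistician. A Beta prior on a rate, set against a column of subject numbers, admits only a yes/no outcome per subject. The dose-escalation table (Protocol Table 4-2) uses the same shorthand: it is headed with a number of DLTs and plainly means subjects, since Protocol 9.4.2.3.1 tabulates DLTs by subject incidence. SAP 9.6.2 likewise reports adverse events, including grade 4 and above, by subject incidence. This stands as evidence of intent. A reader might infer from the explicit wording of Table 9-4 that Table 9-2 deliberately means events; given Table 4-2, the documents do not support that.

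The plan also limits repeat counting. Protocol Appendix 4 tells sites that when severity changes they should "record as a single event with the worst severity on the Event CRF". Protocol 8.4.6 generally keeps laboratory abnormalities without clinical significance out of the adverse event record. Section 6.2.2.1.3 bars restarting tarlatamab after most treatment-related grade 4 events. These provisions make a mean of 2 an upper-end assumption. They do not stop two different grade 4 events in one subject from both counting.

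The practical consequence is limited too. Meeting the limit brings a DLRT review, with continuation unchanged as one outcome. Section 6.2.2.1.4 separately pauses enrolment on small numbers of grade 4 or 5 product-related events, and step 4 does not model that rule, so its figures are not the added halts in practice. Enrolment ended in January 2023 (Protocol 4.1), before the current protocol and SAP were dated.

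All of this lowers the stakes. None of it corrects the unit printed in the two tables.

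**Conclusion.** The point holds as a mismatch between the printed counting unit and the rule. The limits 4/6/9 and the operating characteristics are arithmetically right for subjects with at least one qualifying event; the column heading names a different count. Taken literally, the table halts at least as often as stated.

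A reader might go further and infer that expansion would be halted far too often. The documents do not establish that. The excess is zero if each affected subject has exactly one qualifying event. At a true subject rate of 20% it is about 11 points at a mean of 1.1 (36.4% against 25.8%) and about 40 points at 1.5 (65.5% against 25.8%), and nothing in the documents places the mean within that range. Nor do they show that any halt was wrongly triggered.

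The conclusion rests on the inferred looks at 10, 20 and 30 with a maximum of 40, which the match to Table 9-3 supports, and, for size only, on the assumed distribution of events per affected subject. With enrolment closed, the remaining effect is on how the safety interims are described and whether the boundary is reported as crossed.

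**What to change.** In Protocol Table 9-2 and SAP Table 4, reword the column heading to: *number of subjects with at least one grade 4 or higher treatment-related TEAE*. Leave the limits, the prior, the cutoff and the operating-characteristics tables as they are.

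When reporting the safety interims, give that subject count at each look beside the limit. If the count used at the time was of events, say so and show both. The cost is one column heading in each of two tables and a line in the report. If the protocol is not to be amended again, a clarifying sentence in the SAP and the study report would serve the same purpose.

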9.4.1.1.1 Criteria for Evaluating Treatment With Siltuximab

Amgen will conduct evaluations of the treatment and outcome of the CRS events treated with siltuximab on an ongoing basis to assess if the threshold for evaluating siltuximab treatment has been reached as outlined in the Table 9-4. If these criteria are met, an adhoc DLRM will be triggered to review safety data and available pharmacokinetic, pharmacodynamics, and efficacy data. If recommended by DLRT, the use of siltuximab will resume. The criteria to trigger an adhoc DLRM to review siltuximab treatment use a Bayesian approach proposed by Thall et al, 1995; an adhoc DLRM will be triggered if the posterior probability that the CRS progression to grade 3 rate of greater than 20% is > 80% or the posterior probability that the CRS progression to grade 4 rate of greater than 7.5% is >80%; or observation of any grade 5 CRS after the event has been treated with siltuximab. The boundaries presented below assume a prior distribution of Beta (0.4, 1.6) for progression to grade 3 CRS and a prior distribution of Beta (0.4, 1.6) for progression to grade 4 CRS. The evaluations could occur more frequently if necessary to address emerging safety concerns. If the triggered ad hoc DLRM coincides with regular DLRM, they may be combined.

Table 9-4. The Criteria for Evaluating the Use of Siltuximab

	Trigger DLRM if severity of any CRS event treated with siltuximab progresses to Grade 5					
Number of subjects treated with siltuximab	Or this number of subjects with severity of CRS progressed to Grade 3 after being treated with siltuximab	Or this number of subjects with severity of CRS progressed to Grade 4 after being treated with siltuximab				
	≥ 3	≥ 2				
	≥ 4	≥ 2				
	≥ 5	≥ 3				
	≥ 6	≥ 3				
	≥ 7	≥ 4				
	≥ 9	≥ 4				
	≥ 10	≥ 5				
	≥ 11	≥ 5				

CRS = cytokine release syndrome; DLRM = Dose Level Review Meeting

Protocol Number: 20200439

Date: 05 June 2024 Page 110 of 176

9.4.1.2 Primary Analysis

The primary analysis for this study will occur when target enrollment is complete and each subject either completes at least 6 months on study or withdraws from the study.

9.4.1.3 Final Analysis

The final analysis will be performed after the last subject has had an opportunity to complete the corresponding EOT visit/procedures.

9.4.2 Methods of Analyses

9.4.2.1 General Considerations

Descriptive statistics will be provided for selected demographics, safety, pharmacokinetic, efficacy data by dose, dose schedule, and time as appropriate. Descriptive statistics on continuous data will include means, medians, standard deviations, and ranges, while categorical data will be summarized using frequency counts and percentages. Graphical summaries of the data may also be presented. Confidence intervals (CI) for proportions will be estimated using an exact method proposed by Clopper-Pearson (Clopper and Pearson, 1934). Kaplan-Meier methods will be used to estimate the median and percentiles for time to event endpoints with CI calculated using the Brookmeyer and Crowley (Brookmeyer and Crowley, 1982) method. Kaplan-Meier methods will be used to estimate landmarks for time to event endpoints (eg, 1-year OS) with the Greenwood formula (Kalbfleisch and Prentice, 1980) used to estimate the standard error used in CI calculation.

9.4.2.2 Efficacy Analyses

Endpoint	Statistical Analysis Methods					
Primary	Not applicable					
Secondary	The proportion of subjects with an objective response and disease control (per modified RECIST v1.1) and 95% CI will be tabulated by planned dose level and schedule.					
	For all subjects treated at the recommended phase 2 dose, Kaplan-Meier methods will be used to estimate for 1) duration of response (DOR), 2) OS, 3) progression-free survival (PFS) with 95% CI. For all subjects treated at the recommended phase 2 dose, Kaplan-Meier methods will be used to estimate landmarks for time to event events (eg, 6-month PFS and OS) with 95% CI.					
Exploratory	Will be described in the statistical analysis plan finalized before database lock					

Protocol Number: 20200439

Date: 05 June 2024 Page 111 of 176

9.4.2.3 Safety Analyses

9.4.2.3.1 Analyses of Primary Safety Endpoint(s)

Endpoint	Statistical Analysis Methods
Primary	The analysis of DLTs will be conducted on the DLT Analysis Set. Subject incidence of DLT will be tabulated by planned dose level.
Secondary	The statistical analysis methods for other safety endpoints are below.

9.4.2.3.2 Adverse Events

Subject incidence of all treatment-emergent adverse events will be tabulated by system organ class and preferred term. Tables of fatal adverse events, serious adverse events, adverse events leading to discontinuation from investigational product or other protocol-required therapies, and significant treatment emergent adverse events will also be provided.

9.4.2.3.3 Laboratory Test Results

The analyses of safety laboratory endpoints will include summary statistics at selected time points by treatment group. Shifts in grades of safety laboratory values between the baseline and the worst on-study value will be tabulated by treatment group.

9.4.2.3.4 Vital Signs

The analyses of vital signs will include summary statistics at selected time points by treatment group. Shifts in vital sign values between the baseline and the worst on-study value will be tabulated by treatment group.

9.4.2.3.5 Physical Measurements

The analyses of physical measurements will include summary statistics at baseline by treatment group.

9.4.2.3.6 Electrocardiogram

The ECG measurements from this clinical study were performed as per standard of care for routine safety monitoring, rather than for purposes of assessment of potential QTc effect. No statistical analyses of ECG measurements are planned.

Protocol Number: 20200439

Date: 05 June 2024 Page 112 of 176

9.4.2.3.8 Exposure to Investigational Product

Subject exposure to investigational product and combination therapy will be summarized using descriptive statistics. The number of cycles of protocol-specified therapy administered will be summarized with an additional breakdown of the number of cycles started. In addition, the duration of therapy, the cumulative dose, and the average dose per administration and relative dose intensity will be summarized. The number and percent of subjects with dose modifications (eg, dose reductions, dose interruptions) and reason for modification will be summarized as well. Subject-level data may be provided instead of the summary if the subject incidence is low or single dose is given.

9.4.2.3.9 Exposure to Concomitant Medication

Number and proportion of subjects receiving therapies of interest will be summarized by preferred term for each treatment group as coded by the World Health Organization, 2018.

